4.3. Which confidence intervals will be reported?

Two-sided 95% confidence intervals will be presented for all efficacy parameters.

4.4. How is compliance defined and assessed?

Compliance is defined as the proportion of prescribed doses actually taken by each patient. Pill-count based compliance is assessed by counting the number of left-over pills in the tablet container and dividing this number by the total number of doses in the treatment regime. Additionally, blood levels of guanabenz are monitored every three months to assess medication adherence. Low outliers will be investigated, as they may indicate non-compliance.

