3.1. What is the study design?

This is an open-label, non-randomized study with a historical control group. All patients enrolled will receive guanabenz at their highest tolerated dose, with a target dose of 2 mg/kg/day, a minimum dose of 1 mg/kg/day, and a maximum dose of 10 mg/kg/day. Guanabenz will be administered as oral capsules once daily before bedtime and in addition to the patient's usual standard of care. The control group consists of historical VWM patients collected from an international longitudinal VWM registry with data collection over 20 years, investigating the natural disease course of VWM.

For more details see pages 41 to 50 of the protocol.

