4.5. How will compliance be presented?

Pill-count based compliance will be reported as the median and 25th and 75th percentiles of the proportion of prescribed doses actually taken by each GBZ participant of the study. Additionally, compliance will be presented by guanabenz blood levels over time. The relationship between (pill-count and blood-level based) compliance and all outcome measures will be examined.

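### SAP 4.4 defines compliance as doses taken, but its pill-count formula counts pills left over

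*SAP*

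**What the plan says.** Section 4.4 gives a definition and then a way of measuring it. The definition is: "Compliance is defined as the proportion of prescribed doses actually taken by each patient". For pill counts, the measurement is "counting the number of left-over pills in the tablet container and dividing this number by the total number of doses in the treatment regime". The section adds a second, separate measure: "blood levels of guanabenz are monitored every three months to assess medication adherence".

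Section 4.5 says what will be reported for pill counts: the "median and 25th and 75th percentiles of the proportion of prescribed doses actually taken by each GBZ participant of the study". It also gives compliance a further use: "The relationship between (pill-count and blood-level based) compliance and all outcome measures will be examined".

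On the form of the drug, section 3.1 says: "Guanabenz will be administered as oral capsules once daily before bedtime". Dosing there is per kilogram of body weight, at each child's highest tolerated level. The SAP gives neither a capsule strength nor the number of capsules in a daily dose.

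**The concern.** Pills left in the container are the ones that were not taken. A ratio with that count on top rises as adherence falls, whereas the definition in 4.4 and the reporting statement in 4.5 both describe a quantity that rises with adherence. The definition and the formula cannot both be followed.

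Two planned outputs depend on the pill-count figure: the descriptive summary, and the examination of compliance against outcomes. If the formula is programmed literally, good adherence appears as very poor adherence. The pill-count and blood-level analyses could then point in opposite directions for no reason other than a coding rule. In a small single-arm study with historical controls, adherence helps in interpreting either a null or a favourable result, so the summary should be right.

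There is a second, smaller fault. The numerator is in pills and the denominator is in doses. If a daily dose can be more than one capsule, the ratio is not a proportion of anything, and taking its complement does not recover compliance.

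**Working it through.** The SAP states no compliance figure, so there is nothing to reproduce. The check compares the formula with the SAP's own definition.

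**Notation.** D = doses prescribed; c = capsules per dose; S = capsules supplied; L = capsules left over; capsules taken = S − L.

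- Definition (4.4, repeated in 4.5): C = (S − L) / (cD)
- Formula as written (4.4): R = L / D

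**Step 1: simplest case.** Assume c = 1 and S = D. Then C = (D − L)/D and R = L/D = 1 − C. Take D = 365 (assumed: one dose a day for a year).

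| Left over, L | Definition, (365 − L)/365 | Formula as written, L/365 |
|---|---|---|
| 0 | 100% | 0% |
| 18 | 95.1% | 4.9% |
| 36 | 90.1% | 9.9% |
| 73 | 80.0% | 20.0% |
| 365 | 0% | 100% |

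The two agree only at 50%.

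**Step 2: summary and association.** Replacing C by 1 − C reflects the quartiles about 50% and reverses the sign of any correlation without changing its size. A simulated example with 30 children (invented data, for illustration only) shows this:

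- Quartiles of 88.1 / 91.9 / 96.3% taken become 3.7 / 8.1 / 11.9%.
- The Pearson correlation with the outcome goes from +0.696 to −0.696.
- The Spearman correlation goes from +0.530 to −0.530.

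**Step 3: is 1 − R a safe repair?** Only if c = 1 and S = D. Fix true compliance at 90% and D = 365, and vary the assumptions that the SAP leaves open. Capsules taken = 0.9 × 365 × c. Fractional counts are kept to hold compliance at exactly 90%.

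| c | S | L | R = L/365 | 1 − R | (S − L)/(365c) |
|---|---|---|---|---|---|
| 1 | 365 | 36.5 | 10.0% | 90.0% | 328.5/365 = 90% |
| 1 | 400 | 71.5 | 19.6% | 80.4% | 328.5/365 = 90% |
| 2 | 730 | 73 | 20.0% | 80.0% | 657/730 = 90% |
| 3 | 1095 | 109.5 | 30.0% | 70.0% | 985.5/1095 = 90% |

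When S = cD, R = c(1 − C). If c differs between children, R therefore depends on capsule count as well as adherence, and 1 − R does too. Only the last column recovers 90% in every row.

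**Step 4: what depends on the pill count.**

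- The analyses in 6.3 (log-rank, Cox and mixed models) use treatment and calendar year, not compliance.
- The populations in 4.8 do not depend on compliance.
- Non-compliance is not among the protocol deviations listed in 4.6.
- The exposure analysis in 6.3 uses a population pharmacokinetic model, not pill counts.

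That leaves only the pill-count summary and the pill-count half of the association in 4.5.

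**The case against.** The strongest case on the other side is that this is a slip of wording. The definition in 4.4 and the reporting statement in 4.5 both name the right quantity, so an analyst would be expected to see that a subtraction was left out. A median near 5% would look wrong at once, particularly beside the blood levels. Where the units agree, the error is an exact complement and easily reversed. The SAP also cites a separate data validation and derivation plan (section 7.2), which is not at hand and may contain the correct formula.

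Most of this stands, and it limits the severity. It does not remove the contradiction: the formula is the only operational rule the SAP gives, and nothing in the SAP corrects it. If the derivation plan is right, the SAP disagrees with it and still needs changing. The ease of detection applies to the gross inversion, not to the units. An analyst who simply takes 1 minus the ratio could report a believable but wrong figure, such as 80% in place of 90%.

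The units point is itself conditional. The SAP uses pill, tablet and capsule loosely, and one capsule may in fact be one dose. The two- and three-capsule rows show what could happen under assumptions; they are not evidence of an error in this trial.

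A reader might infer that reported compliance, and its relation to every outcome, will be inverted. The SAP does not support that. Inversion needs literal coding against two statements of intent, and the blood-level measure does not pass through the formula at all.

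**Conclusion.** The point holds as an internal contradiction in section 4.4. The pill-count formula gives the share not taken, while the definition in 4.4 and the reporting statement in 4.5 call for the share taken. With one pill per dose and supply equal to prescription, 95% taken is computed as 5%. If coded as written under those conditions, the pill-count quartiles are the complement of compliance and the pill-count association with outcomes has the wrong sign. If those conditions fail, the ratio is not the exact complement either, and subtracting it from 1 does not reliably repair it.

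It would be tempting to conclude that the trial's efficacy findings are at risk. They are not, on this document: no primary or secondary treatment comparison and no analysis population uses compliance. Severity is minor to moderate. A descriptive summary and one loosely specified association are exposed, and the correction is trivial.

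**What to change.** In section 4.4, replace the pill-count formula with:

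*Pill-count compliance = (capsules dispensed − capsules returned) / capsules prescribed, over the same period, with all three counts in capsules.*

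This matches the definition, gives 100% for a child who takes everything as prescribed, and does not depend on the number of capsules per dose or on exact supply. Section 4.5 can stay as it is. Check that the derivation plan cited in section 7.2 uses the same formula, and align the two if it does not.

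The cost is one sentence in the SAP and one check of the derivation plan. The formula needs only dispensing, return and prescription counts, and no other analysis changes.

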4.5. How will compliance be presented?

Pill-count based compliance will be reported as the median and 25th and 75th percentiles of the proportion of prescribed doses actually taken by each GBZ participant of the study. Additionally, compliance will be presented by guanabenz blood levels over time. The relationship between (pill-count and blood-level based) compliance and all outcome measures will be examined.

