6.1. How are the outcomes of this study defined?

The primary safety outcome is: All adverse events and serious adverse events collected from the start of study treatment until the end of the study and will be summarized for descriptive purposes.

The primary efficacy outcome is the time of loss of ambulation. Loss of ambulation is defined by the loss of walking with support.

The secondary efficacy outcomes are overall survival, HUI attributes and multiscores. Scores on the Vineland, GMFCS-MLD, ELFC-MLD, GMFM, LIPS, GMFCS, MACS CFCS and EDACS will be considered for descriptive purposes.

Other secondary outcomes are Guanabenz PK/PD parameters in plasma and will be summarized for descriptive purposes. Guanabenz exposure will also be correlated with clinical outcome measures.

For more information, please refer to pages 28 to 32 of the study protocol

6.2. Will any calculations or transformations be used to derive any outcome from the original data?

Disease duration will be calculated from age of onset until date of inclusion, screening, baseline, first day of dosing, end of titration, and visits. Ages will be calculated from the date of birth until date of inclusion, screening, baseline, first day of dosing, end of titration, and visits. Time to loss of walking, with or without support, will be calculated from the day of inclusion until the occurrence of the event.

HUI decision tables are used to generate HUI2 and HUI3 single-attribute utility scores, and applied coding algorithms to obtain overall HUI3 Health Index scores. Overall scores on the Vineland and LIPS will be calculated based on their respective domain scores.

6.3. What analysis method will be used and how will the treatment effects be presented?

For the primary efficacy outcome time to loss of ambulation, a comparison of the guanabenz-treated patients will be made with natural history data, adjusting for calendar year of symptoms onset.

For time to loss of ambulation, patients treated with Guanabenz will be matched to historical controls with a 1:2 matching ratio. The matching criteria are:

- Age of symptoms onset
- Degree of handicap regarding ambulation at comparable disease duration

Other variables might be added if considered crucial.

Primary analysis of the primary efficacy endpoint

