In the primary analysis, treated patients will be compared to their matched historical controls. We will analyze time to loss of ambulation using the Kaplan-Meier method and the log-rank test, considering the presence of clustered data. Next, the Cox proportional hazards model will be used to provide an estimate of the effect size, which will contain treatment and will be adjusted for calendar year of symptoms onset. The effects size will be reported using the Hazard Ratio (HR). We will take matching into account when estimating standard errors.

Secondary analysis of the primary efficacy endpoint

In the secondary analysis, we will use historical controls with different matching procedures and different matching ratios. We will use the Kaplan-Meier method and the log-rank test, considering the presence of clustered data. The Cox model will contain treatment and will be adjusted for calendar year of symptoms onset, reporting the effects size using the Hazard Ratio (HR).

Analysis of secondary efficacy endpoints.

The same methods that we used for the primary analysis will be used for overall survival. The HUI scores will be analyzed using linear mixed models adjusting for treatment and calendar year of age of onset. A population pharmacokinetic model will be used to assess the drug exposure (such as AUC or concentration at steady state) and this will then be used to assess the relationship with clinical outcomes using correlation or regression methods.

Descriptive analysis for primary and secondary safety endpoints

A listing of all adverse and serious adverse events will be presented for the guanabenz-treated participants, including the corresponding date and time of collection.

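### Section 4.5 relates the guanabenz blood level to all outcomes as a compliance measure, although under tolerability-based dosing that level reflects dose and clearance more than compliance

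*SAP*

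**What the plan says.** Section 4.4 gives the definition: "Compliance is defined as the proportion of prescribed doses actually taken by each patient". It adds a second source of information, "blood levels of guanabenz are monitored every three months to assess medication adherence", and says of low values: "Low outliers will be investigated, as they may indicate non-compliance".

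Section 4.5 then goes further. Beside the pill-count summary, "compliance will be presented by guanabenz blood levels over time", and "The relationship between (pill-count and blood-level based) compliance and all outcome measures will be examined".

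Section 3.1 gives each child the highest dose tolerated, "with a target dose of 2 mg/kg/day, a minimum dose of 1 mg/kg/day, and a maximum dose of 10 mg/kg/day".

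Separately, 6.1 states: "Guanabenz exposure will also be correlated with clinical outcome measures". Section 6.3 plans a population pharmacokinetic (PK) model to derive exposure and relate it to clinical outcomes by correlation or regression.

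**The concern.** The definition in 4.4 is relative to each child's own prescription. A blood level is not. Two children who take every capsule have different levels if their doses differ, or if they clear the drug at different rates. Section 4.5 does not divide the level by dose, compare it with an expected level or turn it into an adherence category.

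Dose is also not assigned at random. It follows tolerability, so an unadjusted level can relate to an outcome through whatever links tolerated dose to that outcome, or through clearance, with adherence playing no part. Followed as written, 4.5 could report that better compliance goes with better outcome, or with more adverse events, when the relation is with something else. The pill-count and blood-level versions could also disagree for reasons that have nothing to do with capsules taken.

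The same levels already have a correctly named use in 6.1 and 6.3. Section 4.5 comes close to repeating that exposure analysis under a different label.

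**Working it through.** The SAP gives no figure to reproduce on this point. The check asks how much of the level is compliance.

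**Inputs from the SAP.** Compliance is a proportion of prescribed doses (4.4). Dose is 1 to 10 mg/kg/day with target 2, set by tolerability (3.1). Sample size is 20 to 40 (3.3). No dose adjustment of the level is stated (4.4, 4.5).

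**Assumptions, because the SAP gives no distributions.** Levels are proportional to dose. Adherence is Beta with mean 0.9 and SD 0.1. Clearance is lognormal with CV 30% or 50%. Doses are log-uniform over 1–2, 1–4 or 1–10 mg/kg/day. The three are independent unless stated.

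**1. Equal levels from unequal compliance.** Average level is proportional to dose × adherence: 1 × 1.00 = 2 × 0.50 = 10 × 0.10. A fully compliant child at the minimum dose has the same expected level as a child at the target dose who takes half the doses.

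**2. Share of variance.** log level = log dose + log adherence − log clearance.

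- Var(log dose) = (ln of the dose ratio)²/12: 0.0400 for 1–2, 0.1602 for 1–4, 0.4418 for 1–10.
- Adherence: a + b = 0.9 × 0.1/0.01 − 1 = 8, so a = 7.2 and b = 0.8. Var(log adherence) = trigamma(7.2) − trigamma(8) = 0.0158.
- Var(log clearance) = ln(1 + CV²): 0.0862 at 30%, 0.2231 at 50%.

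| Doses (mg/kg/day) | Clearance CV | Total | Dose | Adherence | Clearance |
|---|---|---|---|---|---|
| 1–2 | 30% | 0.142 | 28% | 11% | 61% |
| 1–2 | 50% | 0.279 | 14% | 6% | 80% |
| 1–4 | 30% | 0.262 | 61% | 6% | 33% |
| 1–4 | 50% | 0.399 | 40% | 4% | 56% |
| 1–10 | 30% | 0.544 | 81% | 3% | 16% |
| 1–10 | 50% | 0.681 | 65% | 2% | 33% |

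**3. Other assumptions.** With adherence uniform on 80–100% or 50–100%, PK CV 30% or 60%, and further dose shapes, dose explains 56–83% over 1–10, 30–62% for doses of 1–4 or centred on 2 with log-SD 0.4, and 10–31% for doses of 1–2 or tightly around 2. Adherence explains about 1–3% when it ranges over 80–100% and 5–24% when it ranges over 50–100%. Even at 24%, dose and clearance together hold the other 76%.

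**4. What could be reported.** Suppose the outcome is unrelated to adherence but correlates 0.3–0.5 with log tolerated dose. By simulation, a one-sided 5% test of the unadjusted level is positive in 12–31% (n = 20) or 17–52% (n = 40) with doses 1–2, and in 27–68% or 45–92% with doses 1–10. With no dose–outcome correlation it stays at about 5%.

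**5. Does dividing by dose cure it?** If dose and clearance are independent, level/dose stays near 5%. Under titration to tolerability, slow clearers may stop at lower doses. Take a dose–clearance correlation of 0.5, a dose–outcome correlation of 0.5, n = 40 and two-sided 5% tests. With doses 1–2, level/dose is then positive in about 30–33%, against 6–9% for the unadjusted level. With doses 1–10 the unadjusted level is the worse of the two, at about 64–85%. The gain in tracking adherence is also small near the target: with doses 1–2 and independence, the rank correlation with adherence is 0.19–0.27 before dividing and 0.21–0.32 after.

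**The case against.** Four objections carry weight.

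*The level need not be mainly dose.* A reader might infer from the 1–10 mg/kg/day range that the blood level mostly reflects dose. The SAP does not support that. The target is 2, and a log-uniform spread over 1–10 would put 1 − log10(2) = 70% of children above it. With doses of 1–2, clearance dominates (61–80%) and dose explains only 14–28%. This stands. What survives is that dose and clearance together outweigh adherence.

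*No such test is planned.* A reader might take the positive rates in step 4 as the plan's error rates. They are not. Section 4.5 says only that the relation will be examined. The one-sided 0.05 rule in 4.1 concerns treated participants against historical controls, and the rates need an assumed dose–outcome correlation. They show a mechanism and no more.

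*The derivation may be elsewhere.* Section 4.5 does not exclude a derived measure, and 7.2 cites a data validation and derivation plan that is not shown. That is fair. But 4.5 presents compliance as the levels themselves, so the unadjusted level is the natural reading, and on the other reading the SAP leaves the measure undefined. The same few lines settle both.

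*Dividing by dose may not help.* This also stands (step 5), and it rules out a between-child level/dose ratio as the main remedy.

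The sentence on low outliers in 4.4 is not part of the criticism. It commits only to investigating them.

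**Conclusion.** The point holds as a mismatch of measure and label. Section 4.4 defines compliance relative to prescribed doses. Section 4.5 relates an unadjusted blood level to all outcomes under that name, while 3.1 lets dose differ between children by tolerability. Under the main assumptions adherence explains about 2–11% of the variance in log level, and up to 24% if adherence ranges as widely as 50–100%. Whether dose or clearance takes most of the rest depends on the doses actually reached, which the SAP does not report. A level–outcome relation could therefore be misread as an effect of compliance.

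The reach is limited to this one supportive analysis among treated children. The matched primary comparison, the adverse-event and stopping results, pill-count compliance and the exposure analyses in 6.1 and 6.3 are untouched. The change is worth making because it is cheap and prevents a wrong sentence in the report. Confidence is medium, since every size above rests on assumed distributions and dose-proportional levels.

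**What to change.** In 4.5:

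- Relate only pill-count compliance to outcomes under the label compliance.
- Move the relation of unadjusted levels to outcomes into the 6.1/6.3 analysis, labelled exposure, and state that it is descriptive because dose follows tolerability.
- Use blood levels for compliance only as a supporting flag for non-adherence. Adjust each level for the dose prescribed at that time, and compare it with the child's own other quarterly values or with the population PK model's individual prediction.
- Show the prescribed mg/kg/day beside each level.
- Do not relate a simple between-child level/dose ratio to outcomes as compliance. It still carries clearance, which may itself be linked to tolerated dose.

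The cost is a few lines and one derived variable. Prescribed doses are already needed for 4.4, the PK model is already planned in 6.3, and no dosing or clinical rule changes. The downside is that a within-child flag misses constant under-dosing: a child who always skips the same share of doses looks stable, and an individual PK prediction can absorb that as faster clearance. Pill count has to cover that case.

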4.6. What are defined as protocol deviations in this study?

Protocol deviations are defined as: deviations from the eligibility criteria, concurrent trial participation, unscheduled visits, visits outside the allowed time window, and missed mandatory procedures (e.g., lumbar puncture or blood spot collection).

4.7. How will protocol deviations be presented in the reporting of this study?

All protocol deviations will be line-listed for the guanabenz treated participants, including the number and percentage experiencing one or more protocol deviations.

4.8. Which analysis populations will be defined?

The intention to treat population includes all guanabenz treated participants, who gave written informed consent and were given the first dose of medication. The safety population includes all patients, regardless of protocol deviations or use of rescue medication, but excludes patients, who received no study medication.

Section 5. Study populations.

5.1. Which data were collected from participants, who were screened for eligibility for inclusion in the study, and how will these data be presented in study reports?

Screening data will include the number of patients screened, the number meeting the inclusion criteria, and the number approached for informed consent. For all screened patients, data on age at time of screening, age of onset, disease duration at time of screening, sex, and disease severity (as defined by ambulation) were collected. We will report the mean and standard deviation of age, the number and percentage of male patients and percentage of patients with loss of walking ability without or with light support. Age at the time of loss of ambulation with support will be presented as the median and range. These statistics will be presented for all screened patients, those meeting the inclusion criteria, and those approached for informed consent.

